9.0 MEASUREMENT OF EFFECT

Quantitative endpoints to assess study objectives are as follows:

9.1 Definitions

- *Feasibility*: The proportion of enrolled patients for whom LEAD RT dose can be successfully administered following MRI-guided planning.
- *Acute toxicity*: Grade 2 or higher treatment-related acute GU/GI toxicity occurring during treatment and within 30 days of completing treatment. The severity of the reactions to the treatment is scored according to the criteria outlined in Appendix II.
- *Late toxicity*: Delayed toxicities are usually related to urinary, rectal, and sexual function. The anticipated urinary and rectal toxicities and severity criteria are shown in Appendix II.
- *Biopsy failure rate*: The proportion of positive biopsy findings among patients without clinical or biochemical failure 2-2.5 years after completing study treatment.
- *Biochemical failure-free interval (BFFI)*: The elapsed time from study enrollment to first documented evidence of biochemical failure ($PSA \geq \text{nadir}+2$). In the absence of biochemical failure, follow-up time will be censored at the date of last documented biochemical failure-free status.
- *Biochemical failure (BF) rate*: The cumulative incidence of BF allowing for competing risk as needed.
- *Biochemical failure-free survival (BFFS)*: The elapsed time from study enrollment to first documented evidence of biochemical failure or death from any cause, whichever occurs first. In the absence of any event defining biochemical failure, follow-up time will be censored at the date of last documented biochemical failure-free status.
- *Failure-free interval (FFI)*: The elapsed time from study enrollment to first documented evidence of biochemical or clinical failure. Clinical failure is defined as local failure due to newly identified extension outside of the prostate after initial regression, or urinary obstructive symptoms with carcinoma found at TURP or regional/distant failure due to radiographic evidence metastasis (nodal or hematogenous spread). In the absence of any event defining failure, follow-up time will be censored at the date of last documented failure-free status.
- *Failure rate*: The cumulative incidence of biochemical or clinical failure allowing for competing risk as needed.
- *Failure-free Survival (FFS)*: The elapsed time from study enrollment to first documented evidence of biochemical or clinical failure or death from any cause, whichever occurs first. In the absence of any event defining failure, follow-up time will be censored at the date of last documented failure-free status.
- *Overall Survival (OS)*: The elapsed time from study enrollment to death from any cause. For surviving patients, follow-up will be censored at the date of last contact.
- *Biomarker expression*: Quantification of the amount of the biomarker specific immunohistochemical staining in the area of tumor
- *QOL*: Two contemporary instruments will be utilized to assess patient function and bother (Expanded Prostate Cancer Index Composite-SF12 (EPIC-SF12)), and prostate cancer-specific anxiety (Memorial Anxiety Scale for Prostate Cancer patients (MAX-PC)).

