2.2 Secondary Objectives

- To measure the risk of leaving tumor cells in the prostate after LEAD RT by obtaining serial post-RT MRI's (3 months and 9 months, and within 2 months of the post-treatment prostate biopsy).
- To quantify biomarker expression in different prostate tumor regions, comparing specifically the multiparametric suspicious and unsuspecting regions.
- To determine the proportion of study patients with positive prostate biopsies at 2-2.5 years after completion of therapy as a preliminary indication of the efficacy.
- To report failure-free (biochemical and clinical progression) and overall survival.
- To assess Health-Related Quality of Life (HRQOL) in the study patients.

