3.3.1 Cancellation Guidelines

If a patient does not receive protocol therapy, the patient may withdraw. Patients who are enrolled on study but not treated with the LEAD component of the protocol will be excluded from all analyses.

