8.0 CORRELATIVE/SPECIAL STUDIES

Prior to treatment during fiducial markers placement, patients who choose to have biopsies will undergo needle biopsy of the prostate. Tissue from paraffin blocks will be used for biomarker quantification and correlative studies with treatment outcome.

At 2-2.5 years after completion of treatment (radiotherapy or androgen deprivation – whichever is longer) all patients, with or without documented failure will undergo needle biopsy of the prostate, unless clinically contraindicated or the patient refuses. . A total of 12-14 biopsy cores, are preferred; although the number could be less if the physician thinks it is not appropriate to continue. Biopsies may be obtained from any suspicious functional MRI areas and/or the original site of biopsy confirmation of prostate cancer at diagnosis. These data will enable us to evaluate the extent of disease eradication, as well as the prognostic significance of positive biopsies in men who are otherwise free of evidence of disease (low PSA and palpably normal prostate gland). The Eigen Artemis® system fusion software (not FDA approved) may be used to fine-tune the location of the tumor and biopsies by fusion of the previously obtained multiparametric MRI to the transrectal ultrasound in real time. The ultrasound is the true guidance imaging parameter that identifies the prostate boundaries and other nearby structures. The MRI is fused to the ultrasound such that the biopsies may be directed to a region in the ultrasound space.

If the research biopsies contain prostate tumor cells, the results will be discussed with the patient and additional management considerations (e.g., rebiopsy) made apart from this clinical trial. Many times tumor cells are seen on prostate biopsies at 2-2.5 yr, but the cells show radiation treatment effect. In this situation, it is reasonable to continue to follow the PSA and rebiopsy a year later to look for clearance of the tumor cells. The strategy to rebiopsy will be up to the treating physician and will not be governed by the protocol.

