14.2 Analysis Plan

Study findings will include descriptive statistics summarizing patient baseline characteristics, RT planning parameters and treatment received⁹⁴. A detailed safety profile will be provided consisting of lists and tabulations of all adverse events indicating type, grade, attribution to treatment and time of onset relative to treatment according to CTCAE standards. This will be done separately for acute and late toxicity (see Section 9.1). Patient level summaries will include worst grade toxicity and the number and duration of treatment delays attributable to toxicity.

Feasibility will be assessed by reporting the proportion of enrolled patients who are administered LEAD dose following successful MRI-guided planning and corresponding 95% confidence interval (CI) using the exact binomial method. The same method will be used to estimate the two-year positive biopsy rate defined as the proportion of positive biopsy findings among patients without clinical or biochemical failure two years after completing study treatment.

Clinical outcome will be further assessed by estimating the rate of biochemical failure, as defined in Section 9.1, using the method of cumulative incidence allowing for competing risk of death without biochemical failure. Biochemical failure free survival will be estimated by the Kaplan Meier method. Similar analysis will be provided for the combined rate of biochemical and clinical failure (cumulative incidence) and failure free survival (Kaplan Meier). Although death of study patients during the planned follow up period is expected to be rare and not attributable to prostate cancer, we include these survival endpoints (biochemical failure-free, failure-free, and overall survival) for completeness.

We will summarize the scores of QOL assessments with descriptive statistics and apply mixed effects modeling to evaluate changes over time.

Finally, to the extent permitted by available data from baseline biopsies, exploratory analysis will be performed to investigate the relationship between the level of biomarker expression in tumor tissue within vs. outside the DCE-MRI determined region and the correlation between these measures and Gleason score. Analysis of the sequential imaging studies will correlate the presence/absence of DCE enhancing area and its volume with biopsy positivity at 2 – 2.5 years. We will attempt to establish the ability of MRI for early assessment of RT outcome.

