APPENDIX I
STUDY CALENDAR

Assessment	Prior to RT	24 hr Post-LEAD RT	Weekly during RT	Follow-up				
				During last week of RT	6 Weeks	3 Mo	Every 6 months thereafter up to 5.25 years post-RT	Other
History & Physical Exam*	X		X	X	X	X	X	
Multiparametric MRI of prostate/pelvis ^a	X					X		At 9 mo, and within 2 mo of 2 yr prostate biopsy
Bone Scan or PET Bone Scan ^b	X							As needed
Prostate Biopsy ^c	X							2 – 2.5 years post completion of all therapy
CT and MRI simulation	X							As needed
PSA ^a	X				X	X	X	
Serum-Testosterone ^d	X			X	X	X		At 9 months after RT
BUN and creatinine						X		At 9 months and within 2 mo of 2 yr prostate biopsy
Liver function tests ^a	X			X	X	X		
Complete blood cell counts ^a	X			X		X		
Lipid Profile ^a	X	X		X	X	X		At 9 months and within 2 mo of 2 yr prostate biopsy
EPIC-SF12 ^e	X			X	X	X		At 9 months, 15 mo and yearly to 5.25 years
MAX-PC ^e	X			X	X	X		At 9 months, 15 mo and yearly to 5.25 years
IPSS ^f	X			X	X	X	X	At each follow-up visit
Start of ADT ^g	X							
Plasma and serum, and urine collection for research ^h	X	X		X	X	X		At 9 months and within 2 mo of 2 yr prostate biopsy

*Toxicity and performance status (Zubrod score) will be assessed at each scheduled history and physical exam visit. Interval history will be obtained during following RT at these visits. On-treatment and follow-up physical exams are focused per routine.

- ^aObtained \leq 3 months of signed consent and complete blood count and liver function tests (LFTS). If ADT is not administered, only pretreatment and 3 month LFTs are required. Lipid panels are preferred to be fasting (not required).
- ^bObtained \leq 4 months of enrollment if PSA >15 ng/mL or Gleason score $8 \geq$ disease. A questionable bone scan is acceptable if other imaging is negative for metastasis. For all others, to be obtained at the discretion of the treating physician.
- ^c The initial biopsy will be carried out during fiducial markers placement (if patient opts to have biopsy), within 4 weeks after enrollment (registration). In follow-up, prostate biopsy will be obtained at first sign of local failure or a rising PSA, or at 2-2.5 years after treatment (after radiotherapy or androgen deprivation – whichever is longer) if no evidence of failure.

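### The biopsy objective (2.2) concerns all study patients, but 9.1 and 14.2 estimate positivity only in men without failure, and no planned analysis gives the stated proportion

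*Combined protocol and SAP*

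**What the plan says.** - **Objective.** Section 2.2 states: "To determine the proportion of study patients with positive prostate biopsies at 2-2.5 years after completion of therapy". It offers this as an early indication of efficacy and does not restrict it by failure status.
- **Endpoint.** Section 9.0 introduces its definitions as the quantitative endpoints for the objectives. Section 9.1 defines the biopsy failure rate as "The proportion of positive biopsy findings among patients without clinical or biochemical failure 2-2.5 years after completing study treatment".
- **Analysis.** Section 14.2 estimates, with an exact binomial 95% confidence interval, the "proportion of positive biopsy findings among patients without clinical or biochemical failure two years after completing study treatment". It says two years where 9.1 says 2-2.5 years.
- **Other use of the late biopsy.** Section 14.2 will "correlate the presence/absence of DCE enhancing area and its volume with biopsy positivity at 2 – 2.5 years". That is a correlation with imaging and promises no rate.
- **Who is biopsied.** Section 8.0 says that "all patients, with or without documented failure will undergo needle biopsy of the prostate, unless clinically contraindicated or the patient refuses". Appendix I footnote c instead calls for biopsy at the first sign of local failure or rising PSA, "or at 2-2.5 years after treatment (after radiotherapy or androgen deprivation – whichever is longer) if no evidence of failure".
- **Analysis base.** Section 3.3.1 says: "Patients who are enrolled on study but not treated with the LEAD component of the protocol will be excluded from all analyses".

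**The concern.** The population changes between the objective and the endpoint, and the plan gives no reason for it. The new population is selected on an outcome observed after treatment. Section 1.4.2 reports that biopsy status at 24-36 months was the strongest independent predictor of biochemical failure in the largest biopsy series it describes, so failure and residual tumor are related. Section 9.1 also counts obstructive symptoms with carcinoma found at TURP as clinical failure. A man with tumor demonstrated in the prostate in that way therefore leaves the rate meant to measure local persistence.

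At stake is the reading of the trial's early efficacy signal, in a study that Section 14.1 describes as a basis for planning a Phase II trial. The only background rate in the protocol, close to 50% with residual tumor cells at 2 years (Section 1.4.2), is worded without a failure-free restriction. Setting the restricted rate beside it may not compare like with like.

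**Working it through.** **Is the stated proportion available elsewhere in the plan?**

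| Planned output | Gives positivity among all study patients? |
|---|---|
| Biopsy rate (9.1, 14.2) | No. Failure-free men only |
| Imaging correlation (14.2) | No. Not restricted by failure, but no proportion or interval is promised |
| Biochemical failure, combined failure, failure-free survival (9.1, 14.2) | No. A positive study biopsy is not an event |
| Response: no rising PSA and negative biopsies (9.3) | No. It is a composite, and 14.2 does not analyse it |

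None does.

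**How far apart can the two rates be?** The plan states no expected biopsy rate, so there is no figure to reproduce. Let N be the men biopsied, f the number of them with failure, r_n the positivity without failure and r_f the positivity with failure. Then

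all-patient rate − restricted rate = (f/N) × (r_f − r_n).

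N = 25 is the planned enrolment (Section 14.1), taking all men as treated and biopsied. The values of f, r_n and r_f are assumptions. With r_n = 40%:

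| r_f | f = 2 | f = 4 |
|---|---|---|
| 75% | 0.08 × 35 = 2.8 points | 0.16 × 35 = 5.6 points |
| 100% | 0.08 × 60 = 4.8 | 0.16 × 60 = 9.6 |
| 40% | 0 | 0 |
| 0% | 0.08 × (−40) = −3.2 | 0.16 × (−40) = −6.4 |

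If only 20 men are biopsied and r_f is 75-100%, the differences are 3.5-6.0 points for f = 2 and 7.0-12.0 for f = 4.

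**Which f is plausible?** Section 1.4.1 gives 73% freedom from biochemical failure at 10 years for the 78 Gy arm of a randomized dose-escalation trial (nadir+2 definition). Under a constant hazard, expected failures by 2.5 years are 25 × (1 − 0.73^0.25) = 1.89. Two is therefore the closer case, and four is only illustrative.

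**Anchoring on the 50% background figure.** If the all-patient rate were 50% (12.5 of 25), the restricted rate would be (12.5 − f × r_f)/(25 − f):

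- f = 2: 11.0/23 = 47.8% (r_f = 75%) or 10.5/23 = 45.7% (100%).
- f = 4: 9.5/21 = 45.2% (75%) or 8.5/21 = 40.5% (100%).

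**In counts, with exact (Clopper-Pearson) 95% intervals, 2 failures:**

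- Restricted: 9/23 = 39.1% (19.7-61.5).
- All men, both failures positive: 11/25 = 44.0% (24.4-65.1).
- All men, neither positive: 9/25 = 36.0% (18.0-57.5).

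Every shift is small against the width of these intervals.

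**The case against.** The best defence is that the plan makes a deliberate partition. Section 9.0 says its definitions put the objectives into operation, and 14.2 repeats the restriction. Footnote c fits the same scheme, with failing men biopsied when they fail and the rest at 2-2.5 years. On this reading failed men are counted in the failure analyses, and the biopsy rate measures occult persistence in the remainder. Section 8.0 supports such a rate through its interest in "the prognostic significance of positive biopsies in men who are otherwise free of evidence of disease".

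That justifies the failure-free rate as one summary. It does not answer the objective in 2.2, nor Section 8.0's companion aim of judging how far disease has been eradicated. The failure analyses do not use the study biopsy, so the all-patient proportion cannot be rebuilt from the planned outputs. The margin of the imaging cross-tabulation could come close, but the plan does not undertake to report it.

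Several other points stand:

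- The direction is not proven. Section 1.4.2 gives no positivity figure for men who had failed before biopsy, and some failures are regional or distant.
- The plan schedules no formal comparison with the 50% figure, and the failure status of that cohort is not described.
- The magnitudes rest on assumptions.
- If footnote c governs, few failed men will have a biopsy at 2-2.5 years, and a new denominator alone will change little.
- Rewording 2.2 to the failure-free population would also remove the mismatch, though the all-patient proportion would then be given up.

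**Conclusion.** The concern holds. Objective and endpoint describe different quantities, and the one in the objective is not estimated anywhere. That follows from the text and needs no assumption.

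The likely consequence is a rate that looks somewhat more favourable than the all-patient rate. With 2 failures among 25 men and the assumed positivities above, the gap is about 3-5 points. It vanishes if there are no failures or positivity is equal, and it can reverse. The fault lies in what is estimated, not in precision. The primary objective, the stopping rules and the sample size are unaffected, so this is a change that should be made to a secondary descriptive endpoint.

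**What to change.** 1. In 9.1 and 14.2, define one headline estimate: patients with a positive biopsy divided by all LEAD-treated patients biopsied at 2-2.5 years after completion of therapy, regardless of failure status, with an exact 95% confidence interval. Use the same time window in both sections. The LEAD-treated base follows Section 3.3.1.
2. Report the number not biopsied in that window, with reasons, by failure status.
3. Report earlier for-cause biopsies (Section 9.2.2, footnote c) separately, because Section 1.4.2 notes that some early positive biopsies later clear. A combined figure with one result per man belongs only in a labelled sensitivity summary.
4. Keep the failure-free rate as a labelled secondary summary for the prognostic question in Section 8.0.
5. Reconcile Section 8.0 with Appendix I footnote c on whether men with documented failure have the 2-2.5-year biopsy. The all-patient rate depends on which applies, and this review does not choose between them.

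The cost is wording in two sections, one reconciliation and a few extra tabulations. The reported rate may be less favourable. If footnote c is the rule retained, failed men will contribute mainly through the for-cause biopsies and the headline rate will lie close to the failure-free rate. That limit should be stated with the result.

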9.2 Guidelines for Evaluation of Measurable Disease

9.2.1 Clinical primary tumor response will be measured by palpation and recorded in the following ways:

- Pretreatment: A qualitative description of the pretreatment tumor status on DRE, if palpable, will be recorded in the patient's chart.
- Post-treatment: The change in palpable tumor extent will be recorded qualitatively using the definitions in Section 9.1

9.2.2 PSA response: In 98% of patients treated with definitive radiotherapy there is a drop in PSA within 3 months. Those patients that have not responded should be investigated to define the site of progression (local-regional vs. distant metastases). In patients that have responded, a rising PSA later heralds relapse. Biochemical failure will be modeled after the Nadir+2 definition.¹⁷ Evaluation of patients with a rising PSA profile will include a bone scan, MRI-pelvis/prostate, and prostate biopsy. ProstaScint scan has not been shown to be consistent for defining relapse pattern and is not recommended.

9.2.3 Nodal relapse will be scored as having occurred when appropriate clinical-radiographic evidence (CT or MRI evidence) of this becomes evident (biopsy proof not required in the presence of a rising PSA).

9.2.4 Hematogenous relapse will be scored as having occurred when appropriate clinical-radiographic evidence, shows this to be so (biopsy proof not required).

9.2.5 Quality of Life: As described in section 1.5, the EPIC-SF12 and MAX-PC questionnaires will be done during the last week of RT, at 6 weeks, 3 months, 9 months, 15 months, and then yearly to 5.25 years after radiotherapy.

9.3 Response Criteria

No evidence of rising PSA and negative biopsies

9.4 Confirmatory Measurement/Duration of Response

N/A

9.5 Progression-Free Survival

N/A

9.6 Response Review

N/A

10.0 MEASUREMENT OF TOXICITY

Acute proctitis and cystitis lasting for up to 4 months after completion of radiotherapy are accompaniments of radiotherapy for carcinoma of the prostate. The severity of these reactions is routinely evaluated during treatment and will be scored according to the criteria outlined in Appendix II. In our extensive experience, grade 3 or 4 acute toxicities are rare.

Delayed toxicities are usually related to urinary, rectal, and sexual function. The anticipated urinary and rectal toxicities and severity criteria are those shown in Appendix II. Other untoward clinical events will, however, also be documented.

11.0 ADVERSE EVENT REPORTING

The descriptions and grading scales found in the revised NCI Common Terminology Criteria for Adverse Events (CTCAE) version 4.0 will be utilized for adverse event reporting. A copy of the CTCAE version 4.0 can be downloaded from the CTEP web site (<http://ctep.cancer.gov/reporting/ctc.html>).

11.1 Definitions

11.1.1 **Adverse events** (AE's) will use the descriptions and grading scales found in the NCI Common Toxicity Criteria in Appendix II.

Adverse events: Any unfavorable and unintended sign (including abnormal laboratory finding), symptom, or disease temporally associated with the use of a medical treatment or procedure, regardless of whether it is considered related to the medical treatment or procedure (attribution of unrelated, unlikely, possible, probable, or definite). Each AE is a unique representation of a specific event used for medical documentation and scientific analysis.

Any laboratory abnormal value that leads to a change in subject management (eg, treatment discontinuation, requirement for additional medication or monitoring) or is considered to be of clinical significance by the investigator should be reported as an AE or SAE as appropriate, unless this value is consistent with the subject's present disease state or is consistent with values obtained prior to entry into the study.

11.1.2 A **serious adverse event** (SAE) is defined in the FDA CFR 312 as any adverse drug experience occurring at any dose that results in any of the following outcomes: death, a life-threatening adverse drug experience, inpatient hospitalization, or prolongation of existing hospitalization, a persistent or significant disability/incapacity, or a congenital anomaly/birth defect.

SAE's are defined by FDA and therefore seriousness (not severity) serves as a guide for defining regulatory reporting obligations for patient/subject safety. **Serious** is based on patient/event outcome or action criteria usually associated with events that pose a threat to a patient's life or functioning. FDA

The definition of serious adverse event (experience) also includes **important medical events**. Medical and scientific judgment should be exercised in deciding whether reporting is appropriate in other situations, such as important medical events that may not be immediately life-threatening or result in death or hospitalization but may jeopardize the patient or **may require intervention** to prevent one of the other outcomes listed in the definition above. These should also usually be considered serious. Examples of such events are intensive treatment in an emergency room or at home for allergic bronchospasm; blood dyscrasias or convulsions that do not result in hospitalization; or development of drug dependency or drug abuse.

11.1.3 **Expected events** are those that have been previously identified as resulting from administration of the agent.

11.1.4 An adverse event is considered **unexpected** when either the type of event or the severity of the event is *not* listed in: the current NCI Agent-Specific Adverse Event List; the investigator's brochure, drug package insert or the drug information section of this protocol.

11.1.5 The definition of **related** is that there is a reasonable possibility that the drug caused the adverse experience.

11.1.6 An **investigational agent** is a protocol drug administered under an Investigational New Drug Application (IND). In some instances, the investigational agent may be available commercially, but is actually being tested for indications not included in the approved package label.

11.1.7 **Commercial agents** are those agents not provided under an IND but obtained instead from a commercial source.

11.1.8 **Concurrent administration:** When an investigational agent(s) is used in combination with a commercial agent(s), the combination is considered to be investigational, and reporting of adverse events would follow the guidelines for investigational agents.

11.1.9 **Sequential administration:** When a study includes an investigational agent(s) and a commercial agent(s) on the same study arm, but the commercial agent(s) is given for a period of time prior to starting the investigational agent(s), reporting of adverse events which occur prior to starting the investigational agent(s) would follow the guidelines for commercial agents. Once therapy with the investigational agent(s) is initiated, all reporting of adverse events should follow the investigational guidelines.

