6.0 DOSING DELAYS/DOSE MODIFICATIONS

6.1 Study Agent

The study agent in this protocol is radiation, to be delivered in an innovative and investigational manner. The experimental component of the treatment is a single high-dose fraction of LEAD radiation, a dose of 12-14 Gy to be delivered to the multiparameter MRI identified tumor lesion(s). As described above, a standard radiation dose used for treatment of prostate cancer is 76 Gy at 2.0 Gy per day. This will be begun the day after the LEAD RT treatment (total dose for all treatments of 88-90 Gy and 149 Gy_{3.0} in 2.0 Gy equivalents).

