7.1.10 Side effects

- **Lupron**: In the majority of patients testosterone levels increased above baseline during the first week, declining thereafter to baseline levels or below by the end of the second week of treatment. The most common side effect of Leuprolide is vasomotor hot flashes; edema, gynecomastia, bone pain, thrombosis, and GI disturbances have occurred. Potential exacerbations of signs and symptoms during the first few weeks of treatment is a concern in patients with vertebral metastases and/or urinary obstruction or hematuria which, if aggravated, may lead to neurological problems such as temporary weakness and/or paresthesia of the lower limbs or worsening of urinary symptoms

- **Zoladex**: During routine screening of Zoladex, no significant pharmacological activity was apparent in the cardiovascular, respiratory, central nervous, renal, metabolic, coagulation or gastric acid secretory systems. Studies have shown that serum levels of testosterone can be reduced and maintained within the castrate range resulting in objective evidence of tumor regression. Other than the occasional transient worsening of cancer symptoms (tumor flare) due to an initial temporary rise in testosterone serum levels on initiating therapy, no significant toxicity apart from that attributed to castration (hot flashes, decreased erections, impotence) has been reported. In general, allergic reactions have been extremely uncommon with Zoladex therapy. There have been isolated reports of urethral obstruction, urticaria, or spinal cord compression.

- **Casodex**: The drug is well tolerated and has good response rates in phase II trials. Non-pharmacological adverse events, reported in the trial using bicalutamide 50 mg as

monotherapy include asthenia, pelvic pain, peripheral edema, pruritus, rash, constipation, impotence, dyspnea, nausea, and pain.⁹³ There has been no observed change in cardiac parameters during long-term administration of bicalutamide 50 mg daily. When bicalutamide 50 mg was given in combination with an LHRH analogue, the LHRH analogue adverse event profile predominated with a high incidence of hot flashes (49%) and relatively low incidences of gynecomastia (4.7%) and breast pain (3.2%), the associated pharmacological effects of bicalutamide monotherapy.⁹³ Bicalutamide or flutamide is recommended during the first month of LHRH agonist treatment.

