- **Eulexin:** The reported side effects of treatment include diarrhea and anemia. A high percentage of patients treated with flutamide alone developed gynecomastia within 2-8 months. There have been post-marketing reports of hospitalization, and, rarely, death due to liver failure in patients taking flutamide. Evidence of hepatic injury included elevated serum transaminase levels, jaundice, hepatic encephalopathy, and death related to acute hepatic failure. The hepatic injury was reversible after prompt discontinuation of therapy in some patients. Approximately half of the reported cases occurred within the initial 3 months of treatment with flutamide.

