11.3.6 IRB Reporting

11.3.6.1 All adverse events that are serious adverse events **and** are unexpected **and** are related or possibly related IRB within ten (10) working days of being made known to the Principal Investigator. Events that are more frequent than anticipate or more severe than expected must be reported to the IRB within ten (10) working days of being made known to the Principal Investigator.

All unanticipated deaths must be reported to the IRB within 24 hours of being made known to the Principal Investigator.

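### Section 11.1.5 ties *related* to a drug although the study agent is radiation, contradicting 11.2.2; read literally, a serious LEAD-caused event fails the IRB reporting test

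*Combined protocol and SAP*

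**What the plan says.** Section 6.1 is explicit: "The study agent in this protocol is radiation, to be delivered in an innovative and investigational manner". The only drugs are the ADT agents. Section 6.2 says they are not specific to the study, and Section 3.1 makes ADT permitted but not required.

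The definitions in 11.1 are nonetheless written for a drug trial:

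- **Serious (11.1.2):** "any adverse drug experience occurring at any dose that results in any of the following outcomes".
- **Unexpected (11.1.4):** the type or the severity of the event is missing from an NCI agent list, the investigator's brochure, or the "drug package insert or the drug information section of this protocol".
- **Related (11.1.5):** "there is a reasonable possibility that the drug caused the adverse experience".

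The only drug information in the protocol is Section 7, on ADT. Section 7.1.10 includes, for goserelin, "There have been isolated reports of urethral obstruction, urticaria, or spinal cord compression" and, for flutamide, "The reported side effects of treatment include diarrhea and anemia". Section 7.1.12, where reported adverse events and potential risks would go, is marked N/A.

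Section 11.3.6.1 applies these definitions. An event goes to the IRB when it is serious, unexpected and, as printed, "are related or possibly related IRB within ten (10) working days of being made known to the Principal Investigator". The same section adds two routes that state no relatedness condition: events that exceed anticipated frequency or expected severity, and unanticipated deaths.

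**The concern.** Toxicity is part of the primary objective, and the experimental component is a radiation technique that Section 1.2 calls novel. If the rule for expedited reporting recognises only drug-caused events, the events of most interest can drop out of it on the wording alone. Section 10.0 describes acute grade 3 or 4 toxicity as rare, so each such event carries weight in 25 men.

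The gap matters most for late events. The stopping guideline in 14.4 covers treatment and the 30 days after it, while follow-up runs to 5.25 years. A serious urinary or rectal event in that later period is outside 14.4, so its expedited handling depends on Section 11.

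**Working it through.** No arithmetic applies. The check sets the relevant sections side by side and applies them to a serious GU or GI event caused by LEAD RT.

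**Step 1: what must an event be related to?**

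| Section | Relation is to |
|---|---|
| 11.1.5 (definition) | the drug |
| 11.2.1 | study therapy |
| 11.2.2, Step 3 | protocol therapy, investigational or commercial |
| 11.3.6.1 (IRB test) | not stated; possible relation is enough |
| 14.4 (stopping guideline) | treatment, with attribution of possible or stronger |

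Section 11.1.5 is the outlier, but it is also the only formal definition of the term. No rule of precedence is printed.

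**Step 2: apply the *related* condition.** Take a man without ADT who has a serious event caused by LEAD RT. He received no ADT drug to which the event could be attributed. Under 11.1.5 it is not related; under 11.2.2, Step 3, it is. The conditions in 11.3.6.1 are joined by *and*, so on the first reading the test fails whatever the answer on expectedness. In a man on ADT the result is less clear-cut, because a possible drug contribution could be argued and would satisfy 11.1.5.

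**Step 3: apply the *unexpected* condition.** Section 11.1.4 offers no radiation source, so the comparison falls on Section 7.

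| Radiation event | Named as an ADT side effect in 7.1.10? | Result under 11.1.4 |
|---|---|---|
| Diarrhea | yes (flutamide), no grade | may be called expected by type; still unexpected if its severity is taken as unlisted |
| Urethral obstruction | yes (goserelin), no grade | the same |
| Proctitis, cystitis (10.0: usual accompaniments of RT) | not by name | unexpected |
| Bleeding requiring transfusion (4.14) | no | unexpected |

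The definition therefore misclassifies in both directions. Some radiation events can be called expected because an unrelated drug causes something similar, while ordinary effects of pelvic radiotherapy count as unexpected.

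**Step 4: combine.** The *related* definition carries the point, since failing it alone is enough. The *unexpected* definition adds a second possible failure only for event types that Section 7 happens to list.

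**The case against.** The strongest reply is that this is leftover template wording that nobody would apply literally. Section 11.2.2 is the operative procedure for expedited reporting, and its Step 3 covers radiation. Section 11.1.3 ties expected events to the agent, which 6.1 says is radiation. Taken strictly, the drug wording in 11.1.2 would mean that no radiation event could even be serious, which cannot be intended. This has force: an experienced investigator would probably follow Step 3. It does not remove the contradiction, because two readers can classify the same event in opposite ways and the text does not settle which is right.

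A second reply is that other safeguards exist, and it stands in part. The two additional IRB routes state no relatedness condition, and under Appendix III the DSMC reviews adverse event data on an ongoing basis. The limits are that the death route covers deaths only, and that the frequency-and-severity route has only general expectations to work from. Section 4.14 says most symptoms are grade 2 or lower, 4.15 reports no acute grade 4 toxicity with IMRT, and 10.0 calls grades 3 and 4 rare. No list is specific to LEAD RT. Appendix III also refers the DSMC to Section 11.0 for assessing adverse events.

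Two stronger readings are tempting, and the documents do not support them:

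- **A reader might infer that the stopping guideline is compromised by the same definition.** It is not. Section 14.4 states its own treatment-related criterion and attribution threshold, and the pause after the first three patients states no relatedness condition.
- **A reader might infer that every serious LEAD-caused GU or GI event fails two of the three IRB conditions.** That is wrong as a general statement. Section 11.1.4 counts unlisted severity as well as unlisted type, and several typical radiation effects are not named in Section 7, so they pass as unexpected.

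**Conclusion.** The point holds as an internal contradiction in a working safety rule. Under the formal definition a serious LEAD-caused event can fail the three-part IRB test; under the procedural step it would meet the relatedness condition. Expectedness of radiation events has no suitable reference and is misjudged in both directions.

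The conclusion rests on reading 11.1.5 as printed and on the absence of any text giving 11.2.2 precedence. It does not assume that any event has gone or would go unreported. The number of events affected cannot be derived from the documents. The interim monitoring in 14.4, the sample size and the planned analyses are untouched. The amendment should be made because the rule concerns safety and the correction is small.

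**What to change.** 1. In 11.1.5, replace *the drug* with *protocol therapy (LEAD RT, the IMRT course, protocol procedures or ADT)*, to agree with 11.2.2.
2. In 11.1.2, make the same substitution in the drug-based wording for serious events.
3. In 11.1.4, judge radiation-attributed events against a radiation reference list that states the expected grade for each event, so that any higher grade counts as unexpected. Use Section 7 only for ADT-attributed events.

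The grades in item 3 are essential. A list taken from 4.14 and 10.0 without them would make obstruction, diarrhea, bleeding, proctitis and cystitis all *expected* and could reduce expedited reporting. Section 14.4 needs no change.

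The cost is a wording amendment to 11.1, a short graded list, and possibly a few more expedited reports.
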